12.5.2 Secondary Endpoints

Key secondary endpoints include:

- Safety of VentaProst dosing regimen
 - Monitoring of AEs, physical examinations, laboratory tests, and electrocardiograms
- Effect of VentaProst dosing regimen on:
 - Cardiovascular Parameters
 - Pulmonary Vascular Resistance (PVR)
 - Pulmonary Arterial Pressure (PAP)
 - Systemic Arterial Pressure
 - Central Venous Pressure (CVP)
 - Pulmonary Capillary Wedge Pressure (PCWP)
 - Cardiac Output (CO)
 - Oxygenation
 - Arterial Oxygen Saturation (SaO_2) or Oxygen Saturation by Pulse Oximetry (SpO_2)
 - Partial Pressure of Oxygen in Arterial Blood (PaO_2)
 - Ventilator Support
 - FiO_2
 - Ventilator pressures
 - Ventilator volumes
 - Duration of intubation
 - Number and type of cardiovascular medications required through end of study

Similar analyses for the primary endpoint will be applied to the key secondary efficacy endpoints.

12.6 Extent of Exposure

Exposure data will be summarized by treatment group using frequencies and percentages.

12.7 Safety Analyses

Safety measurements include AEs, physical examination, vital signs, laboratory tests, and electrocardiograms. Safety data will be summarized by treatment group using frequencies and incidence rates.

12.7.1 Adverse Events

AEs will be classified into standardized medical terminology from the verbatim description (Investigator term) using the Medical Dictionary for Regulatory Activities (MedDRA). AEs will be presented by preferred term nested within System Organ Class. Verbatim description and all MedDRA level terms, including the lower level terms, for all AEs will be contained in the data listings of the CSR.

AEs will be summarized by presenting, for each treatment group, the incidence of AEs. Although a MedDRA term may be reported more than once for a patient, that patient will be counted only one time in the incidence count for that MedDRA term.

Treatment-emergent adverse events (TEAEs) will be analyzed. AEs that are not treatment-emergent will be listed. A TEAE is defined as

- AEs that emerge during treatment, having been absent at pretreatment, or
- Reemerge during treatment, having been present at pretreatment but stopped prior to treatment, or
- Worsen in severity or frequency during treatment relative to the pretreatment state, when the AE is continuous.

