6.3.5 Study Medication Weaning

After VentaProst dose stabilization, patients will be weaned from VentaProst. VentaProst weaning will occur from mechanical ventilation only. If the patient has been extubated and is on institution's standard of care delivery for administering aerosolized Veletri, weaning will occur in accordance with each site's standard of care guideline for weaning of aerosolized Veletri.

Patients on mechanical ventilation will be weaned from VentaProst slowly due to concern that VentaProst is providing significant clinical benefit and to avoid a rebound effect. Doses will be decreased in increments of 20% of the VentaProst equivalent dose, with a minimum of 30 minutes between changes, down to 20% of the dose before discontinuation. The VentaProst weaning process should occur in isolation to other treatment changes (no changes in inotropes, vasopressors or vasodilators). Patients will be observed closely before, during, and after dosing changes. In the event patients demonstrate signs of hemodynamic instability (changes in combined hemodynamic parameters) or a decrease in oxygenation indicated by either arterial or central blood oxygenation saturation during downward titration, the VentaProst dose will be returned to its previous level. Once patients have been stable for at least 15 minutes, repeat attempts at dose reduction may be undertaken. The process will continue until patients are fully weaned from VentaProst.

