8.2 Adverse Events

8.2.1 Definitions

Adverse events are any untoward medical occurrence in a patient administered a pharmaceutical product and which does not necessarily have to have a causal relationship with this treatment. For the purposes of this study, this will include unanticipated medical events in the judgment of the investigator. Expected medical events are untoward clinical occurrences that are perceived by the investigator to occur with reasonable frequency in the day-to-day care of patients who have undergone cardiac surgery with CPB and who are treated in the ICU with mechanical ventilation. Such events will not be considered adverse events unless the investigator considers the event to be associated with study medication, study device, or to be unexpectedly severe or frequent for a patient.

A pre-existing condition or symptom is one that is present at the start of the study and is reported as part of the patient's medical history. A pre-existing condition or symptom should be reported as an AE only if its frequency, intensity or character worsens during study treatment.

All AEs that occur from the time of the first dose of study medication through the End of Study will be recorded and reported as Treatment-Emergent Adverse Events (TEAE). All AEs must be appropriately documented in the patient's medical chart and on the CRFs. When known, investigators should report syndromes rather than list symptoms associated with the syndrome.

All AEs that are ongoing at the conclusion of the study should be followed until: a) resolution/stable sequelae; b) the Investigator determines that it is no longer clinically significant; or, c) the study patient is lost to follow-up. If no follow-up is provided, the Investigator must provide a written justification.

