10.1.5 End of Study (ICU)

Once VentaProst dosing has been discontinued, the patient will undergo the following study-related procedures and evaluations within 24 hours of VentaProst discontinuation:

- Record all concomitant medications
- Record AEs
- Perform comprehensive physical examination
- Obtain vital signs and weight
- Perform 12-lead ECG
- Collect blood for clinical laboratory tests, including serum pregnancy test for women of childbearing potential

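### Sections 8.2.1 and 12.7.1 define treatment-emergent adverse events differently, and events starting after VentaProst stops but before End of Study fall between the two

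*Combined protocol and SAP*

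**What the plan says.** Two sections define a TEAE.

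- Section 8.2.1 (Definitions) sets a time window. AEs from "the first dose of study medication through the End of Study will be recorded and reported as Treatment-Emergent Adverse Events".
- Section 12.7.1 (Adverse Events, under Safety Analyses) sets three alternative conditions. New events are "AEs that emerge during treatment, having been absent at pretreatment". Events that had resolved before dosing must "Reemerge during treatment, having been present at pretreatment but stopped prior to treatment". Continuing events must "Worsen in severity or frequency during treatment relative to the pretreatment state". All three depend on the phrase *during treatment*. No stop time and no post-dose window are given.

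Section 12.7.1 also says that TEAEs are what will be analysed, and "AEs that are not treatment-emergent will be listed".

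End of Study comes after dosing. Sections 10.1.5 and 10.2.4 place its procedures, including AE recording, "within 24 hours of VentaProst discontinuation". Sections 4.3.1 and 4.3.2, and Tables 1 and 2, show VentaProst Treatment and End of Study as separate periods.

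Section 6.3.5 explains that weaning is slow because of concern that "VentaProst is providing significant clinical benefit and to avoid a rebound effect".

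**The concern.** An AE that starts after the last VentaProst dose and before End of Study is treatment-emergent under one section and, read literally, not under the other. The programmer who builds the safety tables will work from section 12, so the narrower rule is the one likely to be applied.

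Safety and tolerability of VentaProst is a secondary objective (section 3.2), and section 2.2.2 reports no earlier clinical trials of the product. In a study of this size, the classification of a single event can visibly change a reported incidence.

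**Working it through.** The plan states no figure on this point, so there is nothing to reproduce. The check compares the two rules, event by event.

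| Onset of the AE | Section 8.2.1 | Section 12.7.1, read literally |
|---|---|---|
| During VentaProst titration, stable dosing or stepwise weaning | TEAE | TEAE, if new, re-emerging or worse |
| After VentaProst stops, up to End of Study, no other epoprostenol | TEAE | Not a TEAE; listed only |
| After VentaProst stops, while on aerosolized Veletri (section 5.4.1) | TEAE | Depends on whether Veletri counts as treatment |
| Part I, on aerosolized Veletri before crossover | Depends on whether Veletri counts as study medication | Depends on the same point |

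The second row is the direct conflict. The third and fourth rows are open because the documents do not settle the status of Veletri. The Synopsis names it as a Part I study treatment, while section 6.1 identifies the study medication as the Flolan component of VentaProst.

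**What falls in the second and third rows.**

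1. *Scheduled safety tests.* In Tables 1 and 2, physical examination, 12-lead ECG and clinical laboratory sampling appear only at Screening and End of Study. Section 8.1.2 makes clinically significant examination changes from Screening AEs, and section 8.2.5 allows the same for laboratory and ECG abnormalities. The only scheduled post-dose tests therefore take place after discontinuation. Unless onset is dated back into the dosing period, an abnormality first found there is outside 12.7.1.
2. *Rebound.* Section 2.1 gives a half-life of about three minutes. Some withdrawal effects can show during the weaning steps, which are on treatment under both rules. Effects of the final step, from 20% of the dose to none, appear after the last dose and are affected.
3. *Conversion.* Section 5.4.1 moves patients with severe mediastinal bleeding or hemoptysis to aerosolized Veletri, allows it for inadequate response, and moves patients after extubation. Their later events fall in the third row.

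One limit applies to 8.2.1 as well. For pre-existing conditions it requires worsening during study treatment, so it uses the same undefined term there. The clear conflict concerns new events.

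**Scale.** Input: about 10 patients per part (section 5). One patient whose only AE falls in the disputed interval changes the TEAE incidence for that part by 1/10 = 10 percentage points. If the two parts were pooled, the change would be 1/20 = 5 points. This shows how sensitive the table is; it does not estimate how many such events will occur.

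**The case against.** The best defence is that the two sections can be read together: 8.2.1 gives the time window and 12.7.1 says how an event must differ from the pre-dose state. On that reading *during treatment* simply contrasts with pretreatment. Section 4.6 helps a little, because it places the end-of-study assessments at the end of treatment. This is a possible reading, but nothing in the text states it. The separate Treatment and End of Study periods point the other way, and so does the provision in 12.7.1 for AEs that are not treatment-emergent. It is fair to call the root of the problem an undefined term.

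Several stronger readings are tempting, and the documents do not support them.

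- *That these events vanish from the report.* They are recorded at End of Study and listed under 12.7.1, and section 12.3 promises individual patient listings. With about 10 patients per part, a listing can be read case by case. Section 12.7.1 also speaks of summarising the incidence of AEs without restricting that to TEAEs, so it is not certain that they would be absent from every table.
- *That this is the window in which rebound would appear.* It is only part of it. Events during stepwise weaning are TEAEs under both rules, and the pharmacodynamic measurements 15 to 30 minutes after discontinuation are separate from the AE tables.
- *That a large fraction of events is lost.* One could set 4 hours against 24 hours of treatment (4/28 = 14%) or 24 against 24 (24/48 = 50%). These are shares of clock time, not of events. They fix an open-ended treatment duration at 24 hours and read the stated length of the End of Study period as a minimum interval after the last dose, whereas sections 10.1.5 and 10.2.4 give only a maximum.

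Section 12.1 also defers detail to a Statistical Analysis Plan to be finalised before database lock. That plan could resolve the conflict, but no such resolution is in the text supplied.

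**Conclusion.** The conflict is real. Two stated rules classify the same post-discontinuation event differently, and nothing else in the document decides between them. If 12.7.1 is applied literally, AEs starting between VentaProst discontinuation and End of Study leave the TEAE analysis but stay in the listings. The interval matters because it contains the only scheduled post-dose examination, ECG and laboratory tests, and part of the period of possible rebound.

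The conclusion rests on two assumptions: that treatment ends when VentaProst is discontinued, and that abnormalities first found at End of Study are not dated back into the dosing period. The number of events affected cannot be estimated, because the documents give no AE rate or onset pattern. A claim that risk will be understated therefore goes further than the text allows; it may be, by an unknown amount. The primary endpoint is not touched. The point is worth correcting because the tables are small and the correction is cheap.

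**What to change.** Use one definition in both sections: a TEAE is an AE that is new, re-emerges or worsens relative to the pre-dose state, with onset from first dose through End of Study. In the same place:

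- state whether the window opens at the first VentaProst dose or at the first dose of any study treatment;
- state how AEs during aerosolized Veletri are attributed, both before crossover in Part I and after conversion;
- flag onset after VentaProst discontinuation, in the table or the listing, so that possible withdrawal events can be seen.

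The change takes one or two sentences in section 12.7.1 and the Statistical Analysis Plan, with a cross-reference from 8.2.1, and should be made before database lock. It requires no new data and no change in patient management. TEAE counts may be slightly higher as a result.

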12.7.2 Laboratory Values

Clinical laboratory results post-Baseline will be evaluated for markedly abnormal values. For the incidence of markedly abnormal laboratory values, each patient may be counted once in the laboratory parameter value high and in the laboratory parameter low categories as applicable.

12.7.3 Vital Signs

Vital sign values will be evaluated on an individual basis by patient. Abnormal vital sign values will be identified as those outside (above or below) the reference range. Descriptive summary statistics (e.g., mean, SD, median, minimum, maximum) for vital sign parameters and changes from Baseline will be evaluated by treatment group.

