Medication History	X				
Physical Examination	X				X
Vital Signs/Weight/Height	X				X ¹²
12-Lead ECG	X				X
Spirometry	X ¹¹				
Clinical Laboratory Sampling	X				X
Serum Pregnancy Test	X				X
Inclusion/Exclusion Criteria	X	X			
Cardiac Surgery with CPB		X			
Administer Aerosolized Veletri			X ⁶		
Administer VentaProst				X ⁹	
Hemodynamic Parameters ¹		X ⁵	X ^{7,8}	X ¹⁰	
Oxygenation Measurements ²			X ⁷	X ¹⁰	
Ventilator Parameters ³			X ⁷	X ¹⁰	
AE Monitoring ⁴		X			X
Concomitant Medications	X	X			X

¹ Hemodynamic parameters include, but not limited to, Cardiac Index (CI), Cardiac Output (CO), Central Venous Pressure (CVP), Diastolic Pulmonary Arterial Pressure (dPAP), Diastolic Systemic Arterial Pressure (dSAP), Heart Rate (HR), Mean Pulmonary Arterial Pressure (mPAP), Mean Systemic Arterial Pressure(mSAP), Pulmonary Capillary Wedge Pressure (PCWP), Pulmonary Vascular Resistance (PVR), Rhythm, Systolic Pulmonary Arterial Pressure (sPAP), and Systolic Systemic Arterial Pressure (sSAP)

² Oxygenation measurements include SaO₂ or SpO₂ and PaO₂

³ Ventilator parameters include Ventilator Type, Ventilator Mode, FiO₂, Inspiratory Time, Mean Airway Pressure, Peak Inspiratory Pressure, Positive End Expiratory Pressure, and Respiratory Rate

⁴ To include unanticipated medical events in the judgment of the investigator

⁵ Measure hemodynamic parameters prior to cardiac surgery with CPB and prior to dosing with aerosolized Veletri

⁶ Initiate aerosolized Veletri dose at 50 ng/kg/min in accordance with each site's standard of care guidelines and stabilize the patient on aerosolized Veletri for at least 15 minutes

⁷ Measure hemodynamic, oxygenation, and ventilator parameters after stabilization of aerosolized Veletri

⁸ Determination of hemodynamic response from baseline for study inclusion, study continuation, and transition to VentaProst

⁹ Initiate VentaProst dose at the calculated equivalent dose of 17 ng/kg/min; titrate up in 20% increments every 15 minutes (refer to VentaProst Pharmacy Manual); continue until dose is achieved that matches the hemodynamic measurements obtained with aerosolized Veletri dosing; stabilize patient on VentaProst for at least 15 minutes

¹⁰ Measure hemodynamic, oxygenation, and ventilator parameters before and at 15 to 30 minutes after each VentaProst dose (during dosing, stabilization, and weaning [if still intubated]) and at 15 to 30 minutes after discontinuation of VentaProst

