Epoprostenol is metabolized to 6-keto-PGF1 α (formed by spontaneous degradation) and 6,15-diketo-13,14-dihydro-PGF1 α (enzymatically formed), both of which have pharmacological activity at orders of magnitude less than epoprostenol in animal test systems. 6-keto-PGF1 α has been used as a surrogate PK metabolite for epoprostenol, but does not accurately represent the local active concentration of epoprostenol in the lungs with an elimination half-life of approximately 20-30 minutes. Additionally, large and rapid fluctuations in endogenous epoprostenol as indicated by 6-keto-PGF1 α levels perioperatively in cardiac surgery confound the exogenous epoprostenol contribution for PK determinations (Ylikorkala 1981).

Inhalation delivery of epoprostenol in cardiothoracic surgery patients offers an attractive alternative to IV delivery because it minimizes systemic exposure associated with clinically hazardous effects such as hypotension and exacerbation of pulmonary and cardiac shunts. The rationale for administering epoprostenol continuously as an aerosol through ventilator support equipment stems from its extremely short half-life of approximately three minutes *in vivo*. This enables delivery of high local concentrations of vasodilator into the lung vasculature, reducing PVR (pulmonary vascular resistance)

and RH (right heart) afterload. As a result, the use and effectiveness of inhaled epoprostenol is widely reported [Buckley and Feldman, 2010; De Wet, 2004; Fattouch, 2005; Fattouch, 2006; Hache, 2003; Haraldsson, 2001; Khan, 2009; Ocal, 2005] in a variety of applications including mitral valve surgery. Nonetheless, such practices remain off-label, as inhaled epoprostenol is not FDA-approved for this indication or route of administration.

Clinical centers have independently developed protocols to deliver the IV formulation as aerosol by mechanical ventilation and nasal cannula using commercially available nebulizers. The nominally prescribed dose of 50 ng/kg/min is administered without regard for system efficiencies with these protocols. This results in dose delivery to the lungs that is assumed to be within the flat portion of the hemodynamic dose response curve to inhaled epoprostenol.

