2.2.5 Summary of Known and Potential Risks of Inhaled Epoprostenol Administration

Safety of inhaled epoprostenol in cardiothoracic surgery patients is remarkable. In the reported literature to date, there were no reports of serious or life-threatening drug-related safety events. Due to its mechanism of action, inhaled epoprostenol may theoretically cause increased bleeding (anti-platelet mechanism) or systemic vasodilation consequent to spill over into the central circulatory system, but no such events have been reported. Some accounts of the use of inhaled prostacyclin in the chronic setting (e.g. iloprost for PAH) report transient events as listed on the approved product labeling. These include cough, headache, flushing, and an influenza-like syndrome. However, these types of events are unlikely to be reported due to sedation in the ICU setting.

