8.1 General Safety Procedures

8.1.1 Vital Signs and Weight Measurements

Vital sign measurements, including systolic blood pressure (SBP), diastolic blood pressure (DBP), heart rate (HR)[beats per minute], respiratory rate (breaths per minute), and body temperature (in Celsius) will be obtained as clinically indicated. Weight (kg) will be obtained at the time of Screening and at End of Study. Height will be obtained at the time of Screening.

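### The planned vital-sign safety table has no scheduled on-VentaProst value, although systemic pressures and heart rate are already recorded around each dose change

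*Combined protocol and SAP*

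**What the plan says.** - **Analysis.** Section 12.7.3 plans a patient-by-patient check that flags values outside the reference range, and descriptive statistics "for vital sign parameters and changes from Baseline will be evaluated by treatment group". Section 12.7 counts vital signs among the safety measurements. It does not mention the hemodynamic readings.
- **Schedule.** In Tables 1 and 2 the row "Vital Signs/Weight/Height" is marked only at Screening and End of Study. The procedure lists agree: vital signs appear in Sections 10.1.1, 10.1.5, 10.2.1 and 10.2.4, and not in the dosing and weaning lists of Sections 10.1.4 and 10.2.3.
- **Timing of End of Study.** Section 10.1.5 has the patient undergo "study-related procedures and evaluations within 24 hours of VentaProst discontinuation". Section 10.2.4 says the same for Part II.
- **Unscheduled values.** Under Section 8.1.1 vital signs "will be obtained as clinically indicated", with no time points.
- **Risk.** Section 2.2.5 names as a theoretical risk "systemic vasodilation consequent to spill over into the central circulatory system", and adds that no such event has been reported.
- **Data already collected.** The hemodynamic set in Tables 1 and 2 includes systolic, diastolic and mean systemic arterial pressure (sSAP, dSAP, mSAP) and heart rate (HR). For Part I, Table 1 footnote 10 reads "Measure hemodynamic, oxygenation, and ventilator parameters before and at 15 to 30 minutes after each VentaProst dose". Table 2 footnote 7 requires readings before and after each dose change in Part II.
- **PD analysis.** Section 12.5.2 lists systemic arterial pressure as a key secondary endpoint. HR is not on that list. Section 12.3 takes changes from baseline by default, and Sections 10.1.2, 10.2.2 and 12.4 set the hemodynamic baseline before surgery.

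**The concern.** The vital-sign safety table is a natural place to look for a fall in systemic pressure or a rise in heart rate on drug. As scheduled, it compares a value from before the operation with one taken after VentaProst has stopped. Nothing guarantees a value in between.

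This matters because it is the product's first clinical trial (Sections 2.2.2 and 2.2.4). Part II may also keep escalating until pharmacological effects limit the dose (Sections 4.2 and 6.3.4.2). The dose level at which systemic pressure begins to fall is then a main tolerability result. The plan collects the readings that would show it, but the safety analysis does not use them.

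**Working it through.** The plan states no figure on this point, so there is none to reproduce. The check is a count, a decay calculation and a comparison of sections.

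**1. Scheduled on-drug vital signs.** In Table 1 the vital-sign row is blank under the intra-operative, Veletri and VentaProst columns. In Table 2 it is blank under the intra-operative and VentaProst columns. The count during VentaProst is 0 in each part.

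**2. What an End of Study value can carry over.** Section 2.1 gives an "extremely short half-life of approximately three minutes" in vivo, and 2.7 minutes in animals. With first-order decay, the fraction of the last level remaining at time t is 2^(−t / half-life):

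| Time after stopping | Half-life 2.7 min | Half-life 3.0 min |
|---|---|---|
| 15 min | 2^(−5.6) = 2.1% | 2^(−5) = 3.1% |
| 30 min | 2^(−11.1) = 0.05% | 2^(−10) = 0.10% |
| 4 h | 89 half-lives, effectively 0 | 80 half-lives, effectively 0 |

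A fully weaned patient stops from 20% of the dose (Section 6.3.5), so at 15 minutes the residual is 0.2 × 2.1% = 0.4% to 0.2 × 3.1% = 0.6% of the full dose. The End of Study window has an upper limit of 24 hours and no minimum wait. The 15 and 30 minute rows are illustrations, not scheduled vital-sign times.

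**3. What the value may reflect instead.** Section 5.4.1 moves patients to aerosolized Veletri after extubation, so some may be receiving epoprostenol at End of Study, though not as VentaProst. In Part I the End of Study value follows both Veletri and VentaProst, so a change by treatment group cannot be assigned to either.

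**4. What the hemodynamic record offers.** Take a Part I patient with no up-titration and a full wean. The starting dose and the 80, 60, 40 and 20% steps give 1 + 4 = 5 on-drug sets of systemic pressure and HR, plus 1 set after stopping. Each up-titration step adds at least one more. If all of about 10 Part I patients followed that minimal course, there would be at least 10 × 5 = 50 on-drug sets, against 0 scheduled vital signs.

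**5. Whether the PD analysis fills the gap.** It covers systemic pressure but not HR. Its default change runs from before surgery to a dose step after surgery and bypass, so it contains the effect of the operation as well as the drug. A reading before VentaProst exists in both parts. In Part I it is taken on Veletri (Section 10.1.3).

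**The case against.** The strongest reply is that on-drug hypotension has other routes into the results.

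- **Adverse events.** Section 8.2.5 makes a vital-sign abnormality reportable when, for example, it needs intervention or changes study treatment. Adverse events are recorded during dosing (Sections 10.1.4.1 and 10.2.3.1) and summarised under Section 12.7.1.
- **Unscheduled values.** Section 12.7.3 is not restricted to scheduled values and Section 12.3 uses all available data, so a recorded on-drug reading outside the range would be flagged.
- **PD summaries and listings.** Section 12.3 provides minimum and maximum values and individual listings, so extreme pressures are not hidden behind means.
- **Limits of the alternative.** Readings around dose steps are snapshots. In ventilated patients after bypass, a reference range may discriminate poorly and vasoactive drugs move the pressures.
- **Deferred detail.** Section 12.1 leaves detail to an SAP to be finalised before database lock. The document contains no separate SAP text, so what that SAP will tabulate cannot be determined.

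All of this stands, and it rules out a stronger reading. A reader might infer that the trial cannot detect VentaProst-induced hypotension, or that the vital-sign analysis will show none whatever happens. The documents do not support either inference.

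The reply does not close the gap. Section 8.2.1 does not count events expected after cardiac surgery as adverse events unless the investigator links them to drug or device or finds them unusually severe or frequent, so that route depends on judgement. Unscheduled values are prompted by need and cannot support a planned summary by dose. Listings do not specify a change from a pre-VentaProst reading or counts by dose level.

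**Conclusion.** The point holds as a gap in the planned safety tabulation. The Section 12.7.3 analysis has zero scheduled on-VentaProst values in both parts, and its change-from-baseline table is uninformative about systemic vasodilation during dosing. HR is in no planned on-drug summary, and the PD change in systemic pressure mixes surgery and drug unless another baseline is specified. The data needed are already collected.

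This is not a lost safety signal, for the reasons given in the reply above. It is also too strong to say that epoprostenol has cleared in every patient by End of Study. Only VentaProst has been stopped, some patients may be on aerosolized Veletri, and no minimum wait is set.

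The conclusion rests on reading the schedules as complete, which the procedure lists confirm, and on the half-lives in Section 2.1. It assumes that the final SAP does not already add these tables. The count of 5 on-drug sets assumes a full wean on VentaProst. Patients extubated or converted earlier will have fewer.

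**What to change.** In Section 12.7.3 and the SAP, add a safety summary of the sSAP, dSAP, mSAP and HR already recorded around each VentaProst dose change. Report for each patient and by dose level, separately for Parts I and II:

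- the lowest recorded systemic pressures and the extreme recorded heart rates;
- the largest change from the last reading before VentaProst, labelled in Part I as a change from Veletri;
- the number of readings outside the reference range, with the limits stated.

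Assign each reading to the dose running when it was taken. State with the tables that these are spot readings and not true nadirs, and that concomitant vasoactive drugs affect them. Define the baseline for vital signs, which the protocol does for laboratory tests and ECGs (Sections 8.1.3 and 8.1.4) but not here. Keep the Screening to End of Study summary as secondary.

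The cost is revised wording and a few extra tables. No new measurement, patient burden or change in treatment is needed.
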